8.2 Usability validation

In the validation stage, since this is a usability validation only, there is no statistical justification needed for the sample size. The study will enroll at least 30 subjects for this stage.

9 SAFETY AND ADVERSE EVENTS

9.1 Definitions

The definitions for adverse event, adverse device effect, serious adverse event, serious adverse device effect, and unanticipated adverse device effect are provided below (ISO 14155:2011, 21 CFR 812.3(s)).

- Adverse Event (AE): an adverse event is any untoward medical occurrence in a subject which need not be related to the device under investigation.
- Adverse Device Effect (ADE): an adverse device effect is any untoward or unintended response to a medical device which may result from insufficiencies in the instructions for use or deployment of the device, or from use error.
- Serious Adverse Event (SAE): a serious adverse event is an adverse event that results in death, inpatient hospitalization, severe or permanent disability, a life threatening illness or injury, fetal distress, fetal death, a congenital abnormality, a birth defect, or medical or surgical intervention to prevent permanent impairment to body or structure.
- Serious Adverse Device Effect (SADE): a serious adverse device effect is an adverse device effect that results in death, inpatient hospitalization, severe or permanent disability or is life threatening.
- Unanticipated Adverse Device Effect (UADE): any serious adverse effect on health or safety or any life threatening problem or death cause by or associated with, a device, if the effect, problem, or death was not previously identified in

nature, severity or degree of incidence in the investigational plan, or application (including a supplementary plan or application) or any other unanticipated serious problem associated with a device that related to the rights, safety or welfare of subjects. Refer to the Device Risk Analysis and Risk Assessment section for details on anticipated adverse device effects.

9.2 Anticipated Adverse Events:

Sensor may cause slight, temporary redness, which should fade away shortly after sensor removal.

Sensor may cause thermal burn; however, the design includes safeguards and this risk is believed to be minimal. There may be mild allergic reaction to sensor material and adhesives.

9.3 Adverse Event Reporting:

- All Adverse Events, both Anticipated and Unanticipated, must be recorded in the within the CRF and in the Adverse Event Report Form.
- All Adverse Events must be promptly reported to the Sponsor.
- All Unanticipated Adverse Device Effects will be also reported to both the Sponsor and the IRB.
- Both Serious Adverse Events and Unanticipated Adverse Device Effects must be reported to the Sponsor within 48 hours. All other Adverse Events should be reported to the Sponsor within 5 business days.
- All Serious Adverse Events will be also reported to the IRB per IRB reporting requirements. These reports may include, but will not be limited to: date of onset; brief description of the events; their treatment; whether they resulted in death, inpatient hospitalization, severe or permanent disability or were life threatening; their relationship to the study device; and resolution.

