1.1 Background and Rationale

Masimo Corporation is the developer of noninvasive technologies for the measurement and monitoring of physiological variables, such as arterial oxygen saturation (SpO₂), total hemoglobin concentration (SpHb), carboxyhemoglobin concentration (SpCO), methemoglobin concentration (SpMet), acoustic respiration rate monitoring (RAM), and cerebral and regional oximetry (rSO₂, O₃TM). These technologies are noninvasive and have a good patient safety record.

Masimo has developed a new noninvasive sensor named Centroid as a device to aid in preventing hospital-acquired pressure injury or worsening of existing pressure injury by monitoring patient movement, position, and orientation. The sensor is also able to detect falls through the same monitoring features. This type of monitoring may be effective in reducing the debilitating conditions for patients and their extended stays in hospitals, especially in the patient population who are vulnerable to acquire pressure injuries and/or are prone to fall-related injuries.

Each year over 2.5 million individuals in the U.S. develop a pressure injury.¹ Pressure injuries are painful, debilitating and are usually avoidable. Routine repositioning relieves and redistributes pressure over bony prominences. It is a recommended procedure to help mitigate the risks for developing a pressure injury.² The Centroid device, through detection of patient position, is a modality to ensure repositioning occurs routinely.

As many as 1 million Americans fall in the hospital every year. Falls result in fractures, lacerations, bleeding and even death. Current practices to prevent falls include assessment of patient risk, scheduled rounding practices and patient specific interventions to prevent falls.³ The Centroid device is proposed to be an additional technology to assess risk for fall based on patient position and unique modality additive to these current practices.

The Centroid system consists of a wearable, battery-operated, adhesive sensor and a back-end user interface and Root monitor display at the patient bedside as well as a central location (e.g., nursing station). The sensor contains sensing elements [REDACTED] processor, and a blue-tooth communication chip (BTLE 2.4 GHz). An algorithm [REDACTED] calculates the patient's relative position and fall as parameters [REDACTED]

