3 STUDY OBJECTIVES

The primary aim of this study is to collect data for *calibration* and *usability validation* of the new Centroid monitoring system which Masimo has developed for monitoring a patient's position and movement to prevent pressure injury and detecting falls in the hospital. This protocol describes data collection from patient volunteers during their routine hospital stay lasting usually for more than one day. During the calibration phase, positional data will be collected for the purpose of evaluating the Centroid design and technology.

Secondary aims are to collect data for the pulse oximeter sensor and SedLine sensor for the purpose of correlating against Centroid sensor's data and further investigation.

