6 SUBJECT SELECTION AND WITHDRAWAL

6.1 Population Base

Subjects will be at least 18 years of age. Subjects will be recruited from Baylor University Medical Center. A total enrollment of at least 60 unique subjects is targeted.

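### The serious adverse event definition in section 9.1 omits prolongation of an existing hospital stay, although every subject is already an ICU inpatient

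*Combined protocol and SAP*

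**What the plan says.** Section 9.1 defines seriousness twice. For events, "a serious adverse event is an adverse event that results in death, inpatient hospitalization, severe or permanent disability, a life threatening illness or injury"; the list then adds fetal and congenital outcomes and intervention to prevent permanent impairment, and ends. For device effects, "a serious adverse device effect is an adverse device effect that results in death, inpatient hospitalization, severe or permanent disability or is life threatening". Neither list has an open-ended item or mentions a prolonged stay.

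A third category, the UADE, is worded separately. It covers serious device-related effects not already identified in "nature, severity or degree of incidence in the investigational plan", and also any other unanticipated serious device-related problem bearing on subjects' rights, safety or welfare.

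Section 9.3 attaches consequences to these categories. SAEs and UADEs go to the sponsor within 48 hours and also to the IRB. All remaining adverse events have 5 business days to the sponsor. A general rule covers every event: "All Adverse Events must be promptly reported to the Sponsor".

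On the population, section 6.2 requires ICU status. Section 3 describes "data collection from patient volunteers during their routine hospital stay lasting usually for more than one day".

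**The concern.** A subject who is already in an ICU bed cannot readily have an event that results in inpatient hospitalization during 8 to 16 hours of monitoring (section 6.4). The usual reason for that criterion is to pick up events that cost the patient hospital time. In this population such a cost would appear as a longer stay, which the lists do not name. The SAE list was apparently not fitted to these subjects: it keeps fetal and congenital outcomes although section 6.3 excludes pregnancy.

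What is at stake is classification. An event that only lengthens the stay, and is not a UADE, loses the 48-hour limit and the stated route to the IRB. Neither the device data nor the usability evaluation is touched.

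**Working it through.** The plan gives no figure to reproduce. The check is a reading of 9.1 against 6.2, 3 and 9.3, followed by the arithmetic of the two reporting limits.

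**Step 1: classify the event.** Take an adverse event in an ICU inpatient whose only serious consequence is a longer stay.
- SAE list: no death, disability, threat to life, fetal or congenital outcome, or intervention to prevent permanent impairment. The event did not result in hospitalization, because the subject was already hospitalized. Not an SAE.
- SADE list: four items (death, hospitalization, disability, threat to life), none met. Not a SADE.
- UADE: possible only if the event is serious, associated with the device and unanticipated. The definition does not tie the word serious to the SAE list, so a device effect that lengthens the stay may qualify.

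**Step 2: find what is left.** Two groups remain outside SAE and UADE.
- Anticipated device effects, chiefly a burn. Section 9.2 says "Sensor may cause thermal burn; however, the design includes safeguards and this risk is believed to be minimal". It qualifies redness and allergic reaction by severity but gives none for a burn (2 of 3 effects graded). Section 2.3 calls the burn risk low, which is also a likelihood and not a severity. Whether a burn that lengthens the stay is anticipated can be argued either way.
- Events unrelated to the device, which say little about device safety.

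**Step 3: compare the limits in 9.3.** Inputs: 48 hours = 2 calendar days, against 5 business days. Assumptions: both limits are counted in whole days from the event day, and there are no public holidays. Rule A starts counting on the next business day. Rule B counts a weekday event day as day 1. Difference = (calendar days to the fifth business day) − 2.

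| Event day | Rule A: days | Rule A: difference | Rule B: days | Rule B: difference |
|---|---|---|---|---|
| Mon | 7 | 5 | 4 | 2 |
| Tue to Fri | 7 | 5 | 6 | 4 |
| Sat | 6 | 4 | 6 | 4 |
| Sun | 5 | 3 | 5 | 3 |

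Mean difference over the seven event days:
- Rule A: (5×5 + 4 + 3)/7 = 32/7 = 4.6 days.
- Rule B: (2 + 4×4 + 4 + 3)/7 = 25/7 = 3.6 days.

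The range over both rules is 2 to 5 calendar days (48 to 120 hours). These are differences between outer limits. They do not estimate actual delay.

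**Step 4: check which definition drives reporting.** Section 9.3 ties its time limits and IRB reports to SAEs and UADEs. SADEs appear otherwise only in the monitoring checks of section 12.5. The SAE definition is therefore the one with a reporting effect. The report-content list in 9.3 repeats the hospitalization item, again without prolongation, but it is expressly not exhaustive.

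**The case against.** The strongest case on the other side is that little of practical importance falls through.

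- **The UADE route may cover the burn.** A severity that was never stated was arguably never identified, so a burn that lengthens the stay could well be a UADE, with the 48-hour limit and an IRB report. One that needs intervention to prevent permanent impairment is already an SAE. This stands, and it narrows the device-related gap considerably. It does not close it, because 9.1 refers the reader to a risk analysis section for the anticipated effects, and no section is visible under that title. It may mean section 2.3 or text not shown to us, so the point cannot be settled.
- **Other rules bind the investigator.** Section 1 requires adherence to 21 CFR 812, ISO 14155 and ICH GCP. Their wording is not in the documents, and neither are the IRB's own reporting requirements. This stands as a limit: the conclusion concerns 9.1 as written and no more.
- **The delay may be zero.** Events must be reported promptly in any case. A longer stay may become evident only after the sensors are off, when the event may already have been reported. 9.3 does not say when the 48 hours begin. This stands.
- **The rationale is no evidence.** Section 1.1 hopes for "reducing the debilitating conditions for patients and their extended stays in hospitals", but that concerns pressure injuries and falls. It shows that the sponsor regards longer stays as a harm. It does not show an inconsistency with 9.1.

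A reader might infer that such events go unreported, or that serious device harm would be kept from the IRB. The documents do not support either reading. All adverse events are recorded on the CRF and the Adverse Event Report Form and go to the sponsor. The investigator evaluates each one (section 14) and may terminate for a significant event (section 7.5). UADEs go to the IRB. An investigator might also read prolongation into the hospitalization item, but the classification would then depend on the reader.

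**Conclusion.** The point holds for the text of 9.1. The hospitalization criterion is close to empty in a population of ICU inpatients, and an event whose only serious consequence is a longer stay, and which is not a UADE, is non-serious. Its outer limit to the sponsor is later by 2 to 5 calendar days, under the counting assumptions above, and the protocol states no SAE-based IRB report for it. The documents give no frequency for such events, so the number affected cannot be estimated.

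This is a minor safety-reporting correction. It would be going too far to say that the plan departs from the standards it cites, because their wording is not available here. It would also be going too far to treat 2 to 5 days as an expected delay. Study endpoints and device data are unaffected.

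**What to change.** In the SAE definition in 9.1, extend the hospitalization item to read *inpatient hospitalization or prolongation of existing hospitalization*. This is the change that brings in the 48-hour limit and the IRB report. Make the same change in the SADE definition and in the report-content list in 9.3 for consistency; the SADE change alters no deadline. Check that the Adverse Event Report Form, which is not in the documents, uses the same criterion.

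The drafting cost is one phrase in three places, by an amendment signed by investigator and sponsor and approved by the IRB (section 13.4). The running cost is an unknown number of additional 48-hour and IRB reports, probably mostly ICU complications unrelated to the device. As an illustration only: section 6.1 says "A total enrollment of at least 60 unique subjects is targeted". If 1% to 10% of them had such an event (an assumption with no source in the documents), that would be 60 × 0.01 = 0.6 to 60 × 0.10 = 6 additional reports. The criterion will still miss cases in which the longer stay becomes apparent only after participation ends.

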9.4 Deviations from the study protocol

Deviations from the protocol must receive both Sponsor and the investigator's IRB approval before they are initiated with the exception that under emergency circumstances, deviations from the CIP to protect the rights, safety and well-being of human subjects may proceed without prior approval of the sponsor or the EC. Any protocol deviations initiated without Sponsor and the investigator's IRB approval that may affect the scientific soundness of the study, or affect the rights, safety, or welfare of study subjects, must be documented and reported to the Sponsor and to the investigator's IRB as soon as a possible, but no later than 5 working days of the protocol deviation. If protocol deviations continue to occur frequently at a study site, a corrective and preventive action (CAPA) may be opened by the Sponsor.

9.5 Withdrawal of IRB approval

An investigator shall report to the sponsor a withdrawal of approval by the investigator's reviewing IRB as soon as a possible, but no later than 5 working days of the IRB notification of withdrawal of approval.

10 VULNERABLE POPULATIONS

10.1 Definition

10.1.1 Vulnerable populations are defined as disadvantaged sub-segment of the community requiring utmost care, special considerations and protections in research. This study will recruit subjects from the following: economically disadvantaged or unemployed, educationally disadvantaged, and limited English skills and/or Non-US citizens.

10.2 Protection of vulnerable subjects

- There is no compensation provided for economically disadvantaged subjects to eliminate possibility of undue influence due to financial incentive.
- Educationally disadvantaged subjects will be provided ample time to ask questions and comprehend information.

- Subjects with limited English skills and/or Non-US Citizens will be provided translated documents in native language, staff/independent interpreter, and have ample time to ask questions and understand information.
- Medical care will be provided to these subjects after the clinical investigation has been completed if they are injured as a direct result of participating in this research study. The cost of treatment for any research related injury will be covered by Masimo.

10.3 Responsible Parties

- The IRB will review research with vulnerable populations and evaluate consent, level of risk, coercion, and the reason for choosing this particular subject population. The IRB will be responsible for determining what practices will include continuing review for compliance while monitoring these studies.
- The Investigator holds the ultimate responsibility for protecting the rights, safety, and welfare of research subjects by ensuring that all regulations and proper documentation of consent is handled in a compliant and timely manner.

11 DATA MANAGEMENT

11.1 Confidentiality of Records

Information about the patients will be kept confidential. The data will be stored on a password protected database on a secure server, accessible only to the Investigators. Study data that will be released to Masimo and other regulatory authorities will be de-identified and will only pertain to study data collection, demographics, finger location of the sensor, and the recordings from the pulse oximeter.

11.2 Source Documents

Source data is all information, original records of clinical findings, observations, or other activities in a clinical trial necessary for the reconstruction and evaluation of the trial. Source data are contained in source documents. Examples of these original documents and data records include: hospital records, clinical and office charts, laboratory notes, memoranda, recorded data from automated instruments, and copies or transcriptions certified after verification as being accurate and complete. For this study, the case report forms may also be used as source worksheets.

11.3 Case Report Forms

The Site shall capture study data in the CRFs for each subject enrolled. The CRFs will be completed and initial and dated by the PI or delegated personnel. This also applies to those subjects who fail to complete the study. If a subject withdraws from the study, the reason must be noted on the CRF. Case report forms are to be completed on an ongoing basis. CRF entries and corrections will only be performed by study site staff, authorized by the investigator. Entries and corrections to the CRF will be made following Good Documentation Practices.

The CRF will include the following information, including but not limited to: inclusion/exclusion criteria, whether patient consent obtained before start of study, demographic information, device readings, and if occurrence of any adverse event, protocol deviation, and device deficiencies, etc. The CRFs will be signed by the PI to attest that the data is complete and accurate and forward a copy to Masimo.

CRF entries will be verified by study monitor and any errors or inconsistencies will be queried to the site on an ongoing basis. Any changes will be made directly on the paper CRFs and re-verified. Query resolution will be assessed and confirmed by study monitor during site visit. The monitor or study manager will collect original completed and signed CRFs at the end of the study. A copy of the completed and signed CRFs will remain on site

11.4 Data Transfer and Storage

Training on CRF completion will be provided to study personnel prior to data collection. Original CRFs will be stored in a secure location at site. Original CRFs will be scanned and sent to sponsor. [REDACTED]

[REDACTED] device data will be downloaded from the devices and transferred to Masimo using secure file transfer protocols.

CRFs will be checked for accuracy and completeness of data. If there are inconsistent or missing data points, a data query list will be generated and submitted to the PI or designee, who shall both follow GDP practices for data correction by striking through the old entry, adding in new entry with initial and date, and resend to Masimo the corrected CRF. Once all queries have been resolved, Masimo engineers are notified that data is ready for analysis. To ensure data integrity, Masimo engineers will only have read access to study data, therefore are unable to unintentionally tamper with the original data files.

11.5 Record Retention

All study information, including but not limited to study correspondence, study logs, device accountability records, consent forms, subject records, and copies of CRFs should be maintained in the Investigator site files.

Study records shall be retained during the study and for a minimum of two years after date of study closure or date when records are not required to support 510(k) clearance. The Institution's own retention policies and regulations may apply in addition to the minimal requirement.

The Sponsor is responsible for verifying study data, retaining records, analyzing data, and authoring study reports.

12 MONITORING PLAN

12.1 As the Sponsor of this clinical investigation, Masimo Corporation is required by 21 CFR, Part 812, of the Food and Drug Administration regulations to monitor and oversee the progress of the investigation. The monitor(s) assigned by Masimo Corporation to this task will be a direct employee from the Clinical Research department trained on departmental SOPs on conduct and monitoring of Sponsored studies.

12.2 In accordance with good clinical practices guidelines, there will be at least three scheduled monitoring visits to ensure overall regulatory compliance of the study:

[REDACTED]

[REDACTED]

[REDACTED]

12.3 The Investigator shall allow access to all source documents needed to verify the entries in the CRFs and other GCP-related documents (IRB approvals, IRB correspondences, and ICFs) provided that subject confidentiality is maintained in agreement with HIPAA regulations.

12.4 It will be the monitor's responsibility to inspect the CRFs at regular intervals throughout the study, to verify the adherence to the CIP and the completeness, consistency and accuracy of the data being entered on them.

12.5 During each visit, the monitor will also verify presence of informed consent, adherence to the inclusion/exclusion criteria, and documentation of SAEs/SADES and protocol deviations/violations, and check CRF against medical records as necessary.

12.6 After each visit, the monitor will provide a monitoring follow-up letter to the investigator within 4 weeks of visit completion. The follow-up will detail findings and open action items observed during the visit. It is the responsibility of the Principal Investigator and Study Coordinator(s) to respond to the findings of the monitoring report, and complete any open action items as soon as possible but no later than 30 days of receiving the monitoring report. Any open action items not completed within the time allowed may be sufficient grounds for study site

RAMS0006: Calibration and Usability Validation of Patient Monitoring Device for Pressure Injury Prevention and Fall Detection
Version 2.0

suspension or termination; it will be up to the sponsor to determine whether any incomplete action items are sufficient grounds for suspension or termination. See Section 13 for details on suspension and termination.

12.7 Depending on the quality of the data and/or changes to factors affecting patient safety, additional monitoring visits may be necessary according at the sponsor's discretion.

